7. ASSESSMENTS

Every effort should be made to ensure that the protocol-required tests and procedures are completed as described. However, it is anticipated that from time to time there may be circumstances outside of the control of the investigator that may make it unfeasible to perform the test. In these cases the investigator will take all steps necessary to ensure the safety and well-being of the subject. When a protocol-required test cannot be performed, the investigator will document the reason for this and any corrective and preventive actions that he or she has taken to ensure that normal processes are adhered to as soon as possible. The study team will be informed of these incidents in a timely manner.

For samples being collected and shipped, detailed collection, processing, storage, and shipment instructions and contact information will be provided to the investigator site prior to initiation of the study.

7.1. Pregnancy Testing

For female subjects of childbearing potential, a serum pregnancy test with a sensitivity of at least 25 mIU/mL, will be performed at screening. A urine pregnancy test with a sensitivity of at least 25 mIU/mL, will be performed at every site visit including the End of Treatment (EOT) and follow-up visits to confirm the subject has not become pregnant during the study, and at the follow-up visit.

A negative pregnancy test result is required before the subject may receive the investigational product. Pregnancy tests will also be done whenever 1 menstrual cycle is missed during the active treatment period (or when potential pregnancy is otherwise suspected). Pregnancy tests may also be repeated if requested by institutional review boards (IRBs)/ethics committees (ECs) or if required by local regulations.

Urine pregnancy tests must be sensitive to at least 25 mIU/mL and will be conducted with the test kit provided by the central laboratory in accordance with instructions provided in its package insert. Subjects who have missed a menstrual period or who show an indeterminate or positive result on the urine test may not further progress in the study until pregnancy is ruled out using further diagnostic testing (eg, a negative quantitative serum pregnancy test conducted at a certified laboratory).

In the case of a positive confirmed pregnancy, the subject will be withdrawn from administration of investigational product but may remain in the study.

7.3. Safety Assessments

Safety will be assessed by the spontaneous reporting of AEs, physical examinations, vital signs and clinical laboratory results in all subjects who receive at least one dose of the investigational product. Unscheduled safety assessments may be performed at any time during the study to assess any perceived safety concerns. Investigators and Pfizer Clinicians (or designees) will review individual subject data throughout the conduct of the study to ensure subjects' well-being.

7.3.1. Vitals Signs

Vital signs (sitting blood pressure, pulse rate, respiratory rates and temperature) will be measured (pre-dose, if applicable) after 5 minutes of rest as indicated in the Schedule of Activities.

Body temperature will be collected using the tympanic or oral methods and the same method should be used consistently throughout the study.

Blood pressure (BP) will be measured using a standard calibrated blood pressure measuring device. A BP device that uses multiple cuff sizes based on the arm circumference is the required type of device. The appropriate cuff size for the subject must be used to ensure accurate measurement. The arm circumference at the midpoint of the length of the upper arm should be measured to determine the appropriate cuff size in accordance with the specifications of the BP measuring device. The same properly sized and calibrated blood pressure cuff will be used to measure blood pressure each time.

Subjects should be seated in a chair, back supported, and arms bared (free of restrictions such as rolled-up sleeves, etc.) and supported at heart level. Measurements should be taken on the same arm at each visit (preferably non-dominant). Subjects should refrain from smoking or ingesting caffeine during the 30 minutes preceding the measurements. Measurements should begin after at least 5 minutes of rest.

Heart rate should be measured at approximately the same time as BP for a minimum of 30 seconds. When the timing of BP and pulse (heart) rate measurements coincides with a blood collection or other study procedure, BP and pulse (heart) rate should be obtained first.

7.3.2. Medical History, Physical Examination, Height, and Weight

Complete AD disease history includes collection of details of AD at Screening: AD diagnosis, the use of topical treatments, systemic treatments and other treatments for AD. Medical history in addition to AD history including disease duration will be collected at screening. Medical history also includes history of alcohol and tobacco use. Smoking status and average weekly alcohol consumption (units/week) will be collected, where a unit contains 12 g of pure alcohol, an amount equivalent to that contained in 5 oz/150 mL (a glass) of wine, 12 oz/360 mL of beer, or 1.5 oz/45 mL of 90 proof of spirits. Height and weight will be measured without the subject wearing shoes. Height (inches or centimeters) and weight (lb or kg) will be measured and recorded in the source document at the screening

visit. Weight (lb or kg) will continue to be measured and recorded at various time points, see Schedules of Activities.

Complete physical examinations must be performed by the investigator, sub-investigator or a qualified health professional per local guidelines. Complete physical examinations consist of assessments of general appearance; skin; head, eyes, ears, nose and throat (HEENT); mouth, heart; lungs; breast (optional); abdomen; external genitalia (optional); extremities; neurologic function; and lymph nodes.

Targeted physical examinations must be performed by the investigator, sub-investigator or a qualified health professional per local guidelines and should include skin, heart, lungs, and abdomen and examination of body systems where there are symptom complaints by the subject.

Complete and Targeted physical examinations are performed at various time points, see Schedules of Activities.

7.3.3. Chest X-Ray

Chest radiograph (posterior-anterior and lateral views) or other appropriate diagnostic image (ie, computed tomography [CT] or magnetic resonance imaging [MRI]) with no evidence of current, active TB or previous inactive TB, taken at screening or within 12 weeks prior to Study Day 1 and read by a qualified radiologist, are required. Documentation of the official reading must be located and available in the source documentation.

7.3.4. Tuberculosis Testing

At the time of screening, all subjects will undergo tuberculosis (TB) testing unless performed within 12 weeks of Day 1. QuantiFERON®-TB Gold In-Tube Test is the preferred testing method. If the test results are indeterminate, the test should be repeated. If the QuantiFERON®-TB Gold In-Tube test cannot be performed, or if the results of the repeat test are indeterminate, then subjects may be screened using the Purified Protein Derivative (PPD) Tuberculin Skin Test (Mantoux method) with approval of the Pfizer Medical Monitor.

In addition to TB testing as specified in this clinical protocol, a chest X-ray will be performed to aid in TB status determination.

QuantiFERON®-TB Gold In-Tube is an in vitro diagnostic test using a peptide cocktail simulating ESAT-6, CFP-10 and TB 7.7 proteins to stimulate cells in heparinized whole blood. Detection of interferon-gamma by Enzyme-Linked Immunosorbent Assay (ELISA) is used to identify in vitro responses to these peptide antigens that are associated with *Mycobacterium tuberculosis* infection. QuantiFERON®-TB Gold In-Tube is an indirect test for *M. tuberculosis* infection (including disease) and is intended for use in conjunction with risk assessment, radiography and other medical and diagnostic evaluations.

A blood sample (approximately 3 mL) will be collected at screening for QuantiFERON®-TB Gold In-Tube testing. Following sample processing, the sample will be shipped to the sponsor's designated reference laboratory for testing. The procedure for processing and preparing the sample for shipment is described fully in the laboratory manual, which will be provided to investigators.

A negative PPD test can be substituted for the QuantiFERON®-TB Gold In-Tube test only if the central laboratory is unable to perform the QuantiFERON®-TB Gold In-Tube test or cannot determine the results to be positive or negative and the Pfizer Medical Monitor approves it, on a case-by-case basis.

Japan only: While QuantiFERON[®] is the preferred testing method, the T-SPOT[®]. *TB* test is also acceptable as the screening TB test. Like QuantiFERON[®], the T-SPOT[®]. *TB* test is an in vitro diagnostic test for *M. tuberculosis* infection; however, it differs in that it uses a peptide cocktail of ESAT-6 and CFP-10 proteins to stimulate peripheral blood mononuclear cells.

T-SPOT[®]. *TB* testing will be performed at the site's local laboratory. Borderline results from the T-SPOT[®]. *TB* test should be considered exclusionary. If the T-SPOT[®]. *TB* test results are indeterminate, the test should be repeated. If the result of the repeat test is indeterminate, subjects may be screened using the Mantoux/PPD skin test with Pfizer Medical Monitor approval.

Purified Protein Derivative (PPD) Test

If the QuantiFERON[®]-TB Gold In-Tube test or the T-SPOT[®]. *TB* test (Japan only) cannot be performed, or if the results cannot be determined to be positive or negative, then subjects may be screened using the Purified Protein Derivative (PPD) Tuberculin Test (Mantoux method), with the approval of the Pfizer Medical Monitor.

Subjects must have the PPD test administered and evaluated by a health care professional 48 to 72 hours later in order to be eligible for the study, unless performed and documented within the last 3 months. The test should be performed according to local standards with induration of <5 mm required for inclusion.

7.3.5. Electrocardiogram

A single 12-lead ECG will be performed at screening and all other on-site visits as specified in the Schedule of Activities. ECGs reading will be interpreted by a central reader.

All scheduled ECGs should be performed after the subject has rested quietly for at least 10 minutes in a supine position.

A subject's screening ECG must not demonstrate clinically significant abnormalities prior to randomization.

7.3.6. Special Safety Assessment

In the event of a suspected opportunistic infection, effort should be made to identify the pathogen utilizing laboratory or other methods appropriate to the clinical situation.

In case of a suspected viral skin infection (eg, herpes zoster and herpes simplex or eczema herpeticum), a specimen for viral DNA may be analyzed locally for confirmation and results provided to the adjudication committee to support evaluation.

For subjects with a past history of oral or genital HSV and a presentation consistent to prior infections, further laboratory analysis may be performed at the discretion of the investigator.

7.4. Skin Type Assessment

As part of baseline characteristics, a skin type assessment will be done at the Day 1 visit using the Fitzpatrick Skin Type assessment (Refer to Appendix 5). This is used to classify a person's skin type by their response to sun exposure (ie, burning or tanning).

7.5. Assessment of Suicidal Ideation and Behavior

Subjects meeting exclusionary results as described in Section 4.2 on the C-SSRS or PHQ-8 should be excluded from participation; it is recommended the subject's primary care physician (PCP) should be informed, and the subject referred to a mental health professional, either by the PCP or the investigator according to their usual practice.

7.5.1. Columbia Suicide Severity Rating Scale (C-SSRS)

The Columbia Suicide Severity Rating Scale is a validated tool for investigative staff to use to evaluate suicidal ideation and behavior (Appendix 15). At the screening visit, if there are "yes" answers on items 4 or 5 in the past year or on any question in the suicidal behavior section of the C-SSRS in the past 5 years, the subject will not be included in the study. Trained site staff is to administer the C-SSRS to all subjects at screening, score immediately and assess the subject's eligibility based on the answers.

7.5.2. Patient Health Ouestionnaire - 8 items (PHO-8)

The Patient Health Questionnaire -8 items (Appendix 16) is a patient-reported questionnaire consisting of 8 items to assess the subject's depression level. At Screening Visit, if PHQ-8 total score ≥ 15 , the subject will not be included in the study. Site staff is to administer the PHQ-8 to all subjects at screening and score immediately.

7.6. Clinical Laboratory Tests

7.6.1. Blood Volume

Total blood sampling volume planned for this study is approximately 166 mL. Further details regarding the collection, processing, storage, and shipping of the blood samples will be provided in the lab manual.

7.6.2. Laboratory Tests

The following laboratory tests will be performed at time points identified in the Schedule of Activities. Unscheduled clinical labs may be obtained at any time during the study to assess any perceived safety concerns at the investigator's discretion.

Sample collection, labeling, storage, and shipping information can be found in the laboratory manual. All laboratory tests with clinically important changes from baseline identified after administration of investigational product will be followed until the value stabilizes.

Subjects must abstain from all food and drink (except water and non-study medications) for an 8-hour overnight fast prior to labs that include the lipid profile panel on Day 1, Week 4, Week 16, Week 20 and EOS. For all other lab tests, fasting is not required.

Laboratory Tests

Hematology	Serum Chemistry	Urinalysis	Other
Hemoglobin	BUN and Creatinine	рН	HIV^a
Hematocrit	Creatine Phosphokinase	Glucose (qual)	HBsAg ^a
RBC count and indices	Glucose	Protein (qual)	HBcAb ^a
(MCH, MCHC, MCV,	Na+, K+, Cl-, Ca++, P	Blood (qual)	HBsAb ^b
RBC	Total CO2 (Bicarbonate)		HCVAb ^a
Morphology)	AST, ALT	Nitrites	HCV RNA ^b
Reticulocyte count	GGT	Leukocyte esterase	Serum FSH (WONCBP only) or
Platelet count	Total, Indirect & Direct	Microscopy and/or	Pregnancy Test ^{a, c}
WBC count with	Bilirubin	culture ^d	Urine pregnancy test ^c
differential	Alkaline phosphatase		QFT-G or PPD (if applicable) or
Total neutrophils (%, Abs)	Lactate dehydrogenase		T-SPOT [®] . TB test (Japan only) ^e
Eosinophils (%, Abs)	Uric acid		Viral Screen (if applicable)
Monocytes (%, Abs)	Albumin		CCI
Basophils (%, Abs)	Total protein		
Lymphocytes (%, Abs)	Lipid Profile Panel ^f		
Coagulation Panel	Total cholesterol		
Activated Partial	LDL		
Thromboplastin Time	HDL		
(APTT)	Triglycerides		
Prothrombin			
Time/International			HBV DNA
Normalized Ratio			
(PT/INR)			

- At Screening only. HIV testing will be performed for all subjects. Subjects who are positive for HIV will be screen-failed.
- b. HBsAb reflex testing only if HBsAg negative but HBcAb positive. For Japan only: In addition to HBsAg and HBcAb, HBsAb testing will be performed at Screening for all subjects rather than as a reflex test. HCV RNA is reflex testing only if HCVAb is positive. Subjects who are positive for HCVAb and HCV RNA will be screen-failed.
- c. Pregnancy testing for females of childbearing potential; serum FSH for postmenopausal female subjects who have been amenorrheic for at least 12 consecutive months.
- d. Microscopy with culture performed as appropriate.
- e. PPD results should be read within 48 to 72 hours. For Japan only: QFT-G is preferred but T-SPOT[®]. TB test may be performed instead through the site's local laboratory.
- f. Lipid Profile Panel requires at least an 8 hour fast. Lipid profile panel will be completed at Day 1, Week 4, Week 16, Week 20, and EOS, and will include total cholesterol, LDL, HDL, and triglycerides.
- h. For China, Republic of Korea and Taiwan only: Subjects who are HBsAg negative, HBcAb positive, and HBsAb positive at Screening will have reflex testing for Hepatitis B Virus (HBV) DNA. Subjects who have HBV DNA above the lower limit of quantification (LLQ) are excluded. Subjects who have HBV DNA negative or below LLQ may be randomized, but will have HBV DNA testing repeated at Week 12 and Week 20 End of Treatment (EOT) visit, or Early Termination (ET) visit, whichever is sooner. For Japan only: Subjects with negative results for HBsAg, HBcAb and HBsAb tests may be eligible. Subjects who are HBsAg negative, HBcAb negative and HBsAb positive and provide documentation of prior HBV vaccination may be eligible and will not require HBV DNA monitoring during the study. Subjects who are HBsAg negative, HBcAb positive without documentation of prior HBV vaccination AND subjects who are HBsAg negative, HBcAb positive, and HBsAb positive at Screening will have reflex testing for HBV DNA. Subjects who are HBV DNA negative or below LLQ may be randomized but will have HBV DNA repeated at Week 12 and Week 20 End of Treatment (EOT) visit, or Early Termination (ET) visit, whichever is sooner.

Clinically significant abnormal findings should be recorded as AEs. Abnormal test results determined to be caused from laboratory error should not be reported as AEs. Clinically significant laboratory findings at the final assessment should be followed to resolution or until determined by the investigator to be stabilized. Repeat tests may be indicated to establish this. Refer to Appendix 4 for Guidelines on Monitoring and Discontinuation.

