- Use of CYP2C9 and CYP2C19 inducers within 5 half-lives of the inducer plus 14 days of first dose of investigational product. For example, the average half-life of Carbamazepine after repeat dosing is 15 hours. The washout period is calculated as the sum of 5 half-lives (approximately 3 days) and an additional 14 days for a total of 17 days prior to the first dose of investigational product.
- Phototherapy narrowband UVB (NB-UVB) or broadband phototherapy.
- Regular use (more than 2 visits per week) of a tanning booth/parlor.
- Herbal medications with unknown properties or known beneficial effects for AD.

Within 1 week of first dose of investigational product:

• Medicated topical therapy that could affect atopic dermatitis (eg, corticosteroids, calcineurin inhibitors, tars, antibiotic creams, topical antihistamines).

NOTE: Non-medicated topical therapy (ie, emollients), as detailed in Section 5.9.1 are permitted.

Within 1 week of first dose of investigational product:

- Use of CYP2C9 and CYP2C19 inhibitors within 1 week of first dose of investigational product or within 5 half-lives (if known) of the inhibitor, whichever is longer. NOTE: Half-life refers to the half-life of the parent drug and its metabolites, which are inhibitors, as detailed in Appendix 3.
- Anti-platelet drugs.

NOTE: low dose acetyl salicylic acid (≤100 mg QD) is permitted, for the purpose of cardiovascular prophylaxis, at the discretion of the investigator.

- 11. Have a history of any lymphoproliferative disorder such as Epstein Barr Virus (EBV) related lymphoproliferative disorder, history of lymphoma, leukemia, or signs or symptoms suggestive of current lymphatic or lymphoid disease.
- 12. Infection History:
 - a. Have a history of systemic infection requiring hospitalization, parenteral antimicrobial therapy, or as otherwise judged clinically significant by the investigator within 6 months prior to Day 1;
 - b. Have a known helminth infection;

- c. Have active chronic or acute skin infection requiring treatment with systemic antimicrobials within 2 weeks prior to Day 1, or superficial skin infections within 1 week prior to Day 1;
- d. A subject known to be infected with Human Immunodeficiency Virus (HIV), Hepatitis B, or Hepatitis C (Section 7.6.2);

For China, Republic of Korea, and Taiwan only:

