7.6.2.1. Hepatitis Testing

Hepatitis B testing: HB surface antigen (HBsAg), HB core antibody (HBcAb), HB surface antibody (HBsAb).

Subjects will be screened for hepatitis B virus infection. Subjects with hepatitis B surface antigen (HBsAg) negative testing but who test positive for hepatitis B core antibody (HBcAb) must have further testing for hepatitis B surface antibody (HBsAb).

Interpretation of Hepatitis B Testing Results:

- HBsAg negative and HBcAb negative: Subject is eligible for the study;
- HBsAg positive and HBcAb negative: Subject is excluded from study participation;
- HBsAg negative and HBcAb positive and HBsAb positive: Subject is eligible for study;
- HBsAg negative and HBcAb positive and HBsAb negative: Subject is excluded from study participation;
- For China, Republic of Korea, and Taiwan only: Subjects who are HBsAg negative, HBcAb positive, and HBsAb positive at Screening will have reflex testing for Hepatitis B Virus (HBV) DNA. Subjects who have HBV DNA above the lower limit of quantification (LLQ) are excluded. Subjects who have HBV DNA negative or below LLQ may be randomized, but will have HBV DNA testing repeated at Week 12 and Week 20 End of Treatment (EOT) visit, or Early Termination (ET) visit, whichever is sooner;
- For Japan only: In addition to HBsAg and HBcAb, HBsAb testing will be performed at Screening for all subjects rather than as a reflex test. Subjects with negative results for HBsAg, HBcAb and HBsAb may be eligible. Subjects who are HBsAg negative, HBcAb negative and HBsAb positive and provide documentation of prior HBV vaccination may be eligible and will not require HBV DNA monitoring during the study. Subjects who are HBsAg negative, HBcAb negative and HBsAb positive without documentation of prior HBV vaccination AND subjects who are HBsAg negative, HBcAb positive, and HBsAb positive at screening will have reflex testing for HBV DNA. Subjects who are HBV DNA negative or below LLQ may be randomized but will have HBV DNA repeated at Week 12 and Week 20 End of Treatment (EOT) visit, or Early Termination (ET) visit, whichever is sooner;

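### Footnote h of protocol section 7.6.2 names a different Japanese group for reflex HBV DNA testing from criterion 12d, section 6.1, section 7.6.2.1 and schedule footnote aa

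*Protocol*

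**What the plan says.** The Japan hepatitis B rule appears five times in the protocol: Schedule of Activities footnote aa, criterion 12d in section 4.2, section 6.1, footnote h to the laboratory table in section 7.6.2, and section 7.6.2.1.

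Four of the five agree on the first group that goes for reflex HBV DNA testing. Section 7.6.2.1 words it as "Subjects who are HBsAg negative, HBcAb negative and HBsAb positive without documentation of prior HBV vaccination". Criterion 12d, section 6.1 and footnote aa name the same group.

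Footnote h differs. Its two groups are "Subjects who are HBsAg negative, HBcAb positive without documentation of prior HBV vaccination AND subjects who are HBsAg negative, HBcAb positive, and HBsAb positive". In the first group the core antibody result is positive instead of negative, and there is no condition on surface antibody. The footnote goes on: "Subjects who are HBV DNA negative or below LLQ may be randomized but will have HBV DNA repeated at Week 12 and Week 20".

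Three other provisions matter:
- The general list in 7.6.2.1 states: "HBsAg negative and HBcAb positive and HBsAb negative: Subject is excluded from study participation". No Japan paragraph other than footnote h touches this pattern.
- The same list states: "HBsAg negative and HBcAb negative: Subject is eligible for the study".
- Sections 6.2.6 and 6.2.9 ask for the repeat HBV DNA sample only from subjects who were tested at screening.

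**The concern.** The rule decides who may enter and who is monitored on treatment. The rationale given for Amendment 3 is monitoring for hepatitis B reactivation in a country where past exposure is common. Under 7.6.2.1, one HBV DNA result above the limit of quantification ends treatment permanently.

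Footnote h sits under the table that lists the laboratory tests, so a site or laboratory could plausibly take its reflex-test instructions from there. Used alone, it would lead to handling that other current passages do not allow for one serological pattern, and it would omit a test that they require for another. The question is one of eligibility and safety monitoring. No efficacy endpoint, power figure or planned analysis depends on it.

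**Working it through.** There is no planned figure to reproduce. The check sets the two versions of the rule side by side and runs every serological pattern through both.

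**Inputs.** Three results (HBsAg, HBcAb, HBsAb), each positive or negative, and vaccination documents present or absent: 2 × 2 × 2 × 2 = 16 combinations.

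**Rule A** (7.6.2.1; same test groups in 12d, 6.1 and footnote aa). HBV DNA test if
- HBsAg-, HBcAb-, HBsAb+ and no documents, or
- HBsAg-, HBcAb+, HBsAb+.

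**Rule H** (footnote h). HBV DNA test if
- HBsAg-, HBcAb+ and no documents, or
- HBsAg-, HBcAb+, HBsAb+.

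Both versions treat the all-negative subject, and the HBsAg-/HBcAb-/HBsAb+ subject with documents, as possibly eligible without a DNA test. Where the Japan text is silent, the general list in 7.6.2.1 is used.

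**HBsAg positive (8 combinations).** Neither rule calls for a DNA test, so both fall back on the same general list. All 8 agree.

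**HBsAg negative (8 combinations).**

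| HBcAb | HBsAb | Documents | Rule A | Rule H | Agree |
|---|---|---|---|---|---|
| - | - | no | possibly eligible, no test | same | yes |
| - | - | yes | possibly eligible, no test | same | yes |
| - | + | no | DNA test; repeats if randomised | not named; general list gives eligible, no test | **no** |
| - | + | yes | possibly eligible, no test | same | yes |
| + | - | no | not named; general list excludes | DNA test; randomisation possible; repeats | **no** |
| + | - | yes | not named; general list excludes | same | yes |
| + | + | no | DNA test; repeats if randomised | same | yes |
| + | + | yes | DNA test; repeats if randomised | same | yes |

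**Result.** 8 + 6 = 14 combinations agree and 2 differ. The wording of the first group is the only source of the difference: with the same first group in both rules, all 16 agree.

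**Follow-on for the omitted pattern.** For HBsAg-/HBcAb-/HBsAb+ without documents, Rule A gives a screening test and, for those randomised, repeats at Week 12 and Week 20 or early termination. Under footnote h alone there is no screening test. Because 6.2.6 and 6.2.9 tie the repeat sample to a screening test, the repeats drop out as well.

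**Footnote aa.** Its vaccinated group lacks the HBsAb-positive condition that 12d, 6.1, 7.6.2.1 and footnote h carry. Without that condition, the group also takes in HBsAg-/HBcAb-/HBsAb- subjects with documents, but the all-negative sentence already covers them. This is a wording mismatch that changes the handling of no combination.

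**The case against.** The strongest reply is that the harm needs someone to read footnote h and nothing else. Section 4.3 lets a subject be randomised only if no exclusion criterion is met, and section 6.2.1 has the criteria reviewed again on Day 1. Criterion 12d points to section 7.6.2, and that reference takes in subsection 7.6.2.1 with its exclusion list. The omitted pattern must still be tested under the exclusion criterion, the screening procedures, the schedule footnote and the dedicated hepatitis section, so a site following its visit instructions would test it.

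Most of this stands and makes the point smaller. It does not remove it. The reference in 12d reaches footnote h as readily as 7.6.2.1. The exclusion of HBsAg-/HBcAb+/HBsAb- is written only in the general list of 7.6.2.1; the Japan text of 12d does not repeat it.

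A second reply is that the text may have been damaged when the PDF was read. The difference amounts to a few words between look-alike terms. The abbreviation list under the protocol's schedule shows a similar slip, expanding HBsAg as the surface antibody, where the SAP's Appendix 8 defines HBsAg and HBsAb separately. Against this, the footnote h sentence is grammatical and shows no gap or redaction mark. A reading loss cannot be fully excluded, and the source page would settle it.

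**Conclusion.** The inconsistency holds. One of five statements of the Japan rule names a different first group for reflex HBV DNA testing, and the two versions give different results in 2 of 16 combinations. The practical consequences depend on a site or laboratory working from footnote h alone, and on the supplied text matching the source page. The number of Japanese subjects is not given, so no count of affected subjects can be stated.

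A reader might infer more than the documents support:
- *That the two patterns receive opposite handling.* Footnote h does not declare HBsAg-/HBcAb-/HBsAb+ subjects without documents eligible or exempt from testing. It leaves them out, and eligibility comes from the general list.
- *That the protocol permits randomising an excluded subject.* Footnote h's permission does not expressly lift the exclusion in 7.6.2.1, and section 4.3 still applies.
- *That the scheduled tests are lost and a discontinuation event is hidden.* This follows only if four passages requiring the test are disregarded.
- *That the lack of a row for HBsAg+/HBcAb+ in 7.6.2.1 is a further contradiction.* It is a gap in a list. Criterion 12d, on known infection, covers that pattern, and both versions of the rule treat it alike.
- *That the four agreeing passages must be right.* Agreement shows where the conflict lies. It does not establish the clinical intention.

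**What to change.** First compare footnote h with the source page. If the wording is as supplied:
- Reconcile footnote h of 7.6.2 with criterion 12d, section 6.1, section 7.6.2.1 and schedule footnote aa, so that all five name the same groups for reflex testing.
- Reconcile the vaccinated-group wording of footnote aa with the other four passages.
- Notify the Japanese sites.

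The sponsor's clinicians decide the intended rule. The cost is the wording of two footnotes, if footnotes h and aa are the texts changed, and a letter to Japanese sites. No new assay is needed and the SAP does not change.
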